1 PROTOCOL SUMMARY

1.1 SYNOPSIS

Title:	Team-Based Connected Health to Improve Clinical Outcomes and Access in Atopic Dermatitis
Study Description:	This is a pragmatic, randomized, controlled, equivalency trial. This 12- month trial will evaluate the impact of an online, team-based connected health (TCH) model for management of atopic dermatitis (AD) as compared to in-person care. 300 patients will be randomly assigned to the online TCH model or the in-person control arm stratified by two factors: age (<18 years vs. 18+ years) and study site. This pragmatic, randomized trial will compare AD disease severity (Aim 1), quality-of-life and access-to- care measures (Aim 2), and costs (Aim 3) between the two models.
Objectives:	The primary goal of the protocol is to evaluate whether an online, team- based connected (TCH) health model results in equivalent improvements in disease severity and quality of life, provides better access to specialist care, and is cost-saving compared to usual in-person care for AD management. We will perform a pragmatic randomized equivalency trial to compare the online, TCH model versus in-person care. The specific aims of the study are as follows:
	Primary Objective (Aim 1) : Compare differences in AD severity, as measured by the Eczema Area and Severity Index (EASI), Patient-Oriented Eczema Measure (POEM), and validated Investigator Global Assessment (vIGA), between patients randomized to Team-Based Connected Health and in-person care in a 12-month pragmatic, randomized equivalency trial.

Endpoints:	Secondary Objectives (Aim 2): Compare differences in quality of life as measured by dermatology-specific instruments (Dermatology Life Quality Index / Children's Dermatology Life Quality Index) and a generic instrument (European Quality of Life-5 Dimensions) between patients randomized to Team-Based Connected Health and in-person care. Furthermore, we will compare differences in access-to-care measures such as transportation and time needed for evaluation between patients randomized to Team-Based Connected Health and in-person care. Secondary Objectives (Aim 3): Compare differences in healthcare costs from a societal perspective between Team-Based Connected Health and in-person care through cost-minimization analysis. The primary and secondary endpoints are as follows: Primary Endpoint :			
	• Change in EASI from baseline averaged across 12 months.			

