	 Secondary Endpoints: Change in vIGA from baseline averaged across 12 months Change in POEM from baseline averaged across 12 months Change in DLQI and CDLQI from baseline averaged across 12 months Change in EQ-5D-5L and EQ-5D-Y from baseline averaged across 12 months Patient reported access-to-care outcomes, including transportation and time needed for evaluation Healthcare utilization and costs from a societal perspective 			
Study Population:	The study population consists of children and adults (age 1 year and older) with atopic dermatitis (AD). We plan to enroll 300 patients representing the full spectrum of AD disease severity in southern California.			
Description of Sites/Facilities Enrolling Participants:	Ambulatory clinics associated with Keck Medicine of University of Southern California and LAC+USC Medical Centers will participate in enrolling participants.			
Description of Study Intervention:	The Team-Based Connected Health (TCH) model enables structured online interactions among patients, primary care providers (PCPs), and dermatologists. The goal of TCH is to provide patients and PCPs with high-quality online communication with specialists that would otherwise occur in person.			
Study Duration: Participant Duration:	60 months 12 months			

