SecondaryAim 2: Compare differences in quality of life as measured by dermatology-specific instruments (Dermatology Life Quality Index (DLQI)/ Children's Dermatology Life Quality Index (CDQI)) and a generic preference-based instrument (European Quality of Life-5 Dimensions), between patients randomized to TCH and in-person care.Compare differences in access-to- care measures such as transportation and time needed for evaluation between patients randomized to TCH and in-person care.	 The secondary endpoints for Aim 2 include: Change in DLQI or CDLQI from baseline averaged across 12 months between the in-person and online groups Change in EQ-5D-5L or EQ-5D-Y from baseline averaged across 12 months between the in-person and online groups. Transportation and time needed for evaluation between the in-person and online groups. 	monitor AD severity that focuses on the illness as experienced by the patient. The DLQI and the CDLQI are validated, 10- question questionnaires that can be used to assess dermatology- specific quality of life in adults and children with atopic dermatitis. EQ-5D-5L and EQ-5D-Y are validated measures of health status. The EQ- 5D-5L and EQ-5D-Y provide a single index value that can be used for QoL and economic evaluations. Transportation and time needed for evaluation are measures of access.
Secondary		
Aim 3: Compare differences in healthcare costs between TCH and in-person care.	The secondary endpoints for Aim 3 are:Healthcare utilizationHealthcare costs	The Cornell Services Index is a validated method to assess health service use. The measure provides a reliable snapshot of service use patterns across types, providers, and sites of service among adults who seek medical care.

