4 STUDY DESIGN

4.1 OVERALL DESIGN

This study is testing the hypothesis that team-based connected health (TCH) model results in equivalent improvements in disease severity and quality of life, provides better access to specialist care, and is cost-saving as compared to usual in-person care for management of patients with atopic dermatitis (AD).

This is a 12-month, pragmatic, randomized, controlled, equivalency trial to evaluate the impact of an online, team-based connected health (TCH) model for management of atopic dermatitis (AD) as compared to in-person care. A total of 300 participants will be randomly assigned to the online TCH model or the in-person control arm.

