8 STUDY ASSESSMENTS AND PROCEDURES

8.1 EFFICACY ASSESSMENTS

Study investigators and designated study staff will determine patient eligibility during the screening period, using a screening checklist form. Screening can occur on the same day the patient is enrolled if the participant meets the specified inclusion and exclusion criteria.

Outcomes data will be collected using patient-reported, validated instruments as described below.

Assessments and Evaluations (Patient-Report Measures)

- Eczema Area and Severity Index (EASI): the EASI is a validated scoring system that grades the physical signs of atopic dermatitis/eczema. EASI is a core outcome for measuring the clinical signs of eczema in all trials.
- Validated Investigator's Global assessment (vIGA): This is a three-item measure that assesses the thickness, redness, and scale of atopic dermatitis lesions.
- Patient Oriented Eczema Measure (POEM): POEM is a 7-item tool for patient and/or proxy self-completion used to monitor atopic dermatitis severity, focusing on the illness as experienced by the patient.
- Dermatology Life Quality Index (DLQI) or Children's Dermatology Life Quality Index (CDLQI): DLQI/CLDQI is a 10-item survey that asks patients questions about their health-related quality of life on a 0-3 scale. DLQI and CDLQI are routinely used in clinical trials of dermatology treatments and can also be used routinely in clinical practice.
- EQ-5D-5L or EQ-5D-Y: These are generic and utility-based health-related quality of life measures that capture outcomes based on 5 dimensions: mobility, self-care, usual activities, pain/discomfort, and anxiety/depression. Each dimension is measured based on 5 levels: no problems, slight problems, moderate problems, severe problems, and extreme problems.
- Patient reported access-to-care outcomes, including transportation and time needed for evaluation.
- Cornell Services Index: The Cornell Services Index (CSI) assesses the frequency and duration
 of use of a range of services over the past three months. Services are aggregated into four
 types: outpatient psychiatric or psychological, outpatient medical, professional support, and
 intensive services. Each service use includes information on the discipline of the primary
 provider, the location of the service, and the reason for the service. Finally, the CSI collects
 information on out-of-pocket cost to the individual and the primary method of payment (for

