The hypothesis for access-to-care measures is that TCH provides *superior* access to specialist care than in- person model. For these analyses, access-to-care measures include transportation and time needed for evaluation.

Linear regression models will be used to test whether there is a difference between the groups.

Analysis of Costs (Aim 3)

Cost analysis in healthcare research is essential for evaluating the financial impact of different treatment models on both patients and healthcare systems.²⁶⁻²⁷ For this aim, out-of-pocket (OOP) costs represent a significant factor in determining the feasibility and accessibility of team-based connected health (TCH) compared to traditional in-person care for atopic dermatitis (AD). By analyzing OOP expenditures, this study will provide insights into whether TCH offers a cost-effective alternative while maintaining equivalent clinical outcomes.³¹⁻³⁸

Healthcare utilization will be analyzed using the Cornell Services Index (CSI), which quantifies visit frequency, duration, and associated costs for medical, psychological, and professional consultations.³⁰ CSI data will be collected at baseline and again at 12 months, with ITT analysis requiring baseline values to be duplicated for patients missing follow-up data. Visit counts for different service categories will be analyzed through linear models, with treatment status as the primary predictor. Mean visit duration per patient and visit type will be compared across the two groups using Welch's two-sample t-tests and linear regression models incorporating total visit count as a covariate. The impact of TCH on visit duration will be further assessed using analysis of variance (ANOVA) models to determine potential treatment group differences. Additionally, sub-analyses will be conducted to explore whether utilization patterns differ by age or baseline disease severity. Given the pragmatic design of the study, an emphasis will be placed on real-world applicability, ensuring that findings account for the variability seen in routine clinical settings.

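### Aim 3 is set as societal cost, but the only money analysed is patients' out-of-pocket cost, and missing month-12 service-use data are replaced by baseline values

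*Combined protocol and SAP*

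**What the plan says.** **The aim.** Section 1.1 gives Aim 3 as "Compare differences in healthcare costs from a societal perspective between Team-Based Connected Health and in-person care through cost-minimization analysis", and its endpoint list has "Healthcare utilization and costs from a societal perspective". The table in Section 3 words the same aim without a perspective: "Compare differences in healthcare costs between TCH and in-person care". The hypothesis in Section 4.1 is that TCH "is cost-saving as compared to usual in-person care for management of patients with atopic dermatitis". The overall objective in Section 1.1 also includes cost saving, and Section 9.3.1 says the cost-saving hypothesis will be tested with the longitudinal mixed-model technique used for Aims 1 and 2.

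**The data.** The only cost instrument is the CSI, given at baseline and month 12 (Section 1.3) with a three-month recall. Section 8.1 describes its money content as "information on out-of-pocket cost to the individual and the primary method of payment".

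**The analysis.** Section 9.3.3 compares visit counts, visit durations and OOP cost (per visit and overall). It states: "By analyzing OOP expenditures, this study will provide insights into whether TCH offers a cost-effective alternative while maintaining equivalent clinical outcomes". It also says that, under ITT, a patient without follow-up CSI data must have the baseline values reused. OOP cost is first compared by t-tests, then by a multiple linear regression adjusted for site, age, sex, baseline EASI and asthma history, with gamma regression as the sensitivity analysis.

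**The concern.** The objective and the analysis do not measure the same thing. What patients pay is one part of societal cost. It can fall while payer cost or the cost of running the online service rises, so an OOP result cannot settle whether society saves. A paper written to the synopsis could claim more than the data can carry, and cost saving is prominent because it stands in the overall objective and the study hypothesis.

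The missing-data rule is a separate fault. It presents single imputation of a baseline value as something ITT demands. The rule reaches the money outcome too, because OOP cost is recorded inside the CSI.

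A smaller matter is that Section 9.3.1 and Section 9.3.3 name different techniques for Aim 3.

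**Working it through.** The plan gives no sample size, power or effect size for Aim 3. Section 9.1 lists its calculations for the primary endpoint and the Aim 1 and 2 secondaries, so there is no Aim 3 figure to reproduce.

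**1. Objective against analysis**

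| Cost component | Source in the plan | Expressed in money? |
|---|---|---|
| Patient OOP cost | CSI (8.1) | Yes (9.3.3) |
| Method of payment | CSI (8.1) | No, a category and not an amount |
| Visit counts and durations | CSI (8.1, 9.3.3) | No, compared in their own units |
| Transport and time | Aim 2 access measures (9.3.3) | No, compared and not valued |
| Payer or health-system cost | None named, no unit costs | No |
| TCH delivery cost | None named | No |

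Section 9.3.3 says the CSI quantifies costs associated with visits, but Section 8.1 shows that the amount of money collected is OOP cost. No cost-minimization or cost-effectiveness calculation is specified.

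**2. Does ITT require the copying rule?** No. ITT fixes the arm in which a patient is analysed. Section 9.3.2 applies ITT to the primary endpoint with a mixed model that uses whatever follow-up visits exist, without copying baseline.

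The copied value mostly describes care before assignment. Taking three months as 91 days, a CSI completed at the end of the +28-day baseline window in Section 1.3 still has 91 − 28 = 63 of its 91 recall days (69%) before month 0. Section 1.3 does not give the order of the CSI and randomization.

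**3. Effect of copying baseline.** Let b be the common baseline mean, μT and μC the true month-12 means, and dT and dC the shares missing, with missingness unrelated to use within each arm. The expected estimate is

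(1 − dT)μT + dT·b − (1 − dC)μC − dC·b.

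*Equal missingness, dT = dC = m.* This reduces to (1 − m)(μT − μC). With equal SDs at both times and an unadjusted comparison, the 300 patients carry the information of at most 300(1 − m)², against 300(1 − m) with observed data only. The standardised effect is therefore multiplied by √(1 − m). For a difference that observed data would detect with 80% power (two-sided 5%, 1.960 + 0.842 = 2.802), power becomes P(Z > 1.960 − 2.802√(1 − m)).

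| m (assumed) | Share of true difference left | Power instead of 80% |
|---|---|---|
| 5% | 95% | 78% |
| 10% | 90% | 76% |
| 15% | 85% | 73% |
| 20% | 80% | 71% |

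At 15%, 45 of 300 patients carry a copied value. Information is 300 × 0.85² = 217 against 300 × 0.85 = 255, and 2.802 × √0.85 = 2.583 gives power 0.733. The 15% is the planning attrition in Section 9.1. Month-12 CSI missingness is not stated, and the effort in Section 7.2 to collect month-12 data after discontinuation may make it lower.

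*No true difference, unequal missingness.* With μT = μC = μ the estimate is (dT − dC)(b − μ). A gap of 2, 4 or 10 percentage points gives a false difference of 2%, 4% or 10% of the mean change from baseline. For example, suppose both arms fall by 1 visit. With 20% missing on TCH and 10% in person, the false difference is 0.10 × 1 = +0.10 visits; with the shares reversed it is −0.10. It is zero if there is no gap or no change. Gap and change are both assumptions here.

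**4. Models.** Section 9.3.1 assigns Aim 3 to the longitudinal mixed-model technique, whereas Section 9.3.3 uses t-tests, ANOVA, linear regression and gamma regression. None is labelled primary, and baseline OOP cost is not among the covariates named for the OOP regression.

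**The case against.** - **A reader might infer that the plan promises a societal cost-saving result.** It does not. Aim 3 is to compare costs, cost saving is a hypothesis to be tested, and no sentence joins the two ideas. The sentence on cost-effectiveness speaks only of insights. This limits the tone of the criticism, but the societal perspective and cost-minimization are still explicit in Section 1.1 and still have no matching analysis.
- **A reader might infer a commitment to cost-effectiveness analysis** from the remark that the EQ-5D instruments "provide a single index value that can be used for QoL and economic evaluations", or from health-economic terms in the abbreviation list. The remark describes the instruments, and a list of abbreviations commits to nothing.
- **A reader might infer that OOP cost is tested only without adjustment.** Section 9.3.3 calls the t-tests initial and follows them with a regression that includes site and age. What stands is the missing primary label and the disagreement with Section 9.3.1.
- **A reader might infer that the short recall is concealed.** Sections 1.3 and 8.1 state timing and recall openly, and Section 3 says of the CSI: "The measure provides a reliable snapshot of service use patterns". This is a disclosed limitation, not an error.
- **Copying baseline is conservative.** This stands when missingness is equal and unrelated to use: a true difference shrinks and none is created. It fails when missingness differs by arm and use changes over time, and then the direction of the error depends on both. The one Aim 3 sensitivity analysis named, gamma regression, deals with skewness and not with missing data.

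**Conclusion.** Two points hold as written in the plan, and no other section cures them. First, the analysis can show whether patients pay less and use fewer services near month 12; it cannot show that TCH saves cost to society or is cost-effective. This is the main point and rests on the text alone.

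Second, the copying rule is wrongly attributed to ITT. Its size is modest and conditional. The loss from 80% to about 73% power assumes 15% missing in each arm, equal SDs and no adjustment, and it is an illustration because the plan sets no Aim 3 power. The false difference depends on quantities the documents do not give.

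The disagreement over models is minor and is repaired by wording. The point should be corrected before data lock. Nothing here touches the EASI comparison.

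**What to change.** 1. In Sections 1.1, 3, 4.1, 9.3.1 and 9.3.3, restate Aim 3 as patient OOP cost and service use over the three months before the month-12 assessment. Remove the references to a societal perspective, cost-minimization, cost-effectiveness and cost saving in general. Keep a societal claim only if unit costs, TCH delivery cost, and a valuation of patient time and travel are specified before data lock.
2. Delete the rule that copies baseline CSI values. Make the primary analysis one of observed month-12 CSI data by assigned arm, adjusted for the baseline value of the same measure, site and age group. Use multiple imputation by arm as a sensitivity analysis. Baseline carried forward can be a further sensitivity analysis at most.
3. For OOP cost, name the multiple linear regression in Section 9.3.3 as primary. Keep its covariates, use age group, and add baseline OOP cost. Keep gamma regression as the sensitivity analysis. Name one model each for visit counts and visit duration, and correct the Aim 3 sentence in Section 9.3.1 to match.

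These changes need no new data. The price is a narrower stated claim and a little more analysis work. Full societal costing would be real extra work, since the documents give neither unit costs nor the cost of delivering TCH.

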1.2 SCHEMA

1.3 SCHEDULE OF ACTIVITIES (SOA)

Procedures/Assessments	Month 0 / Baseline	Month 3	Month 6	Month 9	Month 12
	+ 28 days	-7 days, +21 days	-7 days, +21 days	-7 days, +21 days	7 days, +28 days
Informed Consent	Х				
Randomization	Х				
Patient or parent/legal guardian					
training on utilization of the	Х				
teledermatology platform					
Baseline Demographics and Medical	x				
History	~				
Atopic Dermatitis Severity Assessments		1	1	1	r
EASI	Х	Х	Х	Х	Х
vIGA	Х	Х	Х	Х	Х
POEM	Х	Х	Х	Х	Х
Quality of Life Assessments			•		
DLQI / CDLQI	Х	Х	Х	Х	Х
EQ-5D-5L / EQ-5D-Y	Х	Х	Х	Х	Х
Access to Care					
Access to Care (Baseline)	Х				
Access to Care (Follow-up)	х	Х	х	х	Х
Healthcare Costs Assessments					
Cornell Services Index	х				Х
Safety Assessments					
Adverse Event Collection Form	Х	Х	Х	Х	Х

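### Utilization and out-of-pocket cost are observed only for about months 9-12 and the cost period is never stated, so Aim 3 cannot support a 12-month cost conclusion

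*Combined protocol and SAP*

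**What the plan says.** The synopsis (1.1) sets the horizon: "This 12- month trial will evaluate the impact of an online, team-based connected health (TCH) model". Its Aim 3 objective reads: "Compare differences in healthcare costs from a societal perspective between Team-Based Connected Health and in-person care through cost-minimization analysis". The matching endpoint is listed as "Healthcare utilization and costs from a societal perspective", with no period attached. The synopsis and section 4.1 both make cost saving part of the trial's overall goal or hypothesis.

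Section 8.1 describes the CSI as recording the amount "of use of a range of services over the past three months" and as collecting "information on out-of-pocket cost to the individual and the primary method of payment". In the Schedule of Activities (1.3), the row "Cornell Services Index" is marked at Month 0 and Month 12 and is blank at Months 3, 6 and 9. Section 9.3.3 agrees: "CSI data will be collected at baseline and again at 12 months".

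Section 9.3.3 then plans between-arm comparisons of visit counts, visit duration, out-of-pocket cost per visit and total out-of-pocket cost. It gives no time period for the totals, no rule for scaling to a year, and no statement that Aim 3 is confined to the last quarter. If the Month 12 form is missing, the baseline value is copied.

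Sections 3 and 9.3.2 define the primary effect as the change from baseline to the average of the follow-up visits from Month 3 to Month 12.

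**The concern.** A cost-minimization analysis takes the two models to be equally effective and then compares what they cost. Here effect would be judged over the Month 3 to Month 12 visits and cost over roughly the last three months, so equivalence on one horizon would be joined to cost on another.

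Because total out-of-pocket cost has no stated period, a reader of a 12-month trial would naturally take it as 12-month cost. Visits in the first nine months are on no CSI form. Sections 2.2.1 and 7.1 allow online-arm patients to seek in-person care or to leave the online intervention. Any cost of doing so before about Month 9 would go unrecorded, and so would any saving made in that time. The planned t-tests, regressions and gamma models cannot recover visits that no form captured.

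**Working it through.** **Inputs.** Recall period: 3 months (8.1). Administrations: baseline and Month 12 (1.3 and 9.3.3). Follow-up: 12 months (1.1). Participants: 300 (4.1). Anticipated attrition: 15% (9.1). The plan states no coverage, power or precision figure for Aim 3, so there is none to reproduce.

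**Step 1: what each form covers.** A form completed at month t covers t - 3 to t.
- Baseline: about months -3 to 0, before the intervention.
- Month 12: about months 9 to 12.
- Follow-up observed: 3 / 12 = 25%. Unobserved: months 0 to 9, 9 / 12 = 75%.

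**Step 2: effect of the visit windows.** The Month 12 window appears to be -7 to +28 days (the minus sign seems lost in the text). Taking 91 days as three months and 30.4 days as one month:
- 7 days early: (365 - 7 - 91) / 30.4 = 8.8 to (365 - 7) / 30.4 = 11.8 months.
- 28 days late: (365 + 28 - 91) / 30.4 = 9.9 to (365 + 28) / 30.4 = 12.9 months.

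A baseline form completed late in its +28-day window could reach up to four weeks past Month 0. The uncovered stretch remains roughly nine months.

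**Step 3: person-time.** Planned follow-up is 300 x 12 = 3,600 person-months. With every Month 12 form returned, 300 x 3 = 900 are observed (25%). Assuming that the 15% attrition applies to all 300 and that each lost participant lacks the Month 12 form, 300 x 0.85 = 255 remain and 255 x 3 = 765 are observed (765 / 3,600 = 21%). The other 45 would contribute only a copied pre-intervention value.

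**Step 4: other sources.** Section 5.4.2 lists severity, quality of life and selected access-to-care measures as the quarterly outcome data; utilization and cost are not listed. Quarterly access forms cover transportation and time, and adverse event forms could reveal hospital stays, but section 9.3.3 uses neither for Aim 3. No claims, billing, chart or platform-log source is named.

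**Step 5: what can be said about the error.** Write the 12-month between-arm difference as D = D(0-9) + D(9-12). Only the second term is observed, and the documents do not constrain the first. As an illustration, let f be the assumed share of D that falls in months 9-12, and suppose a reader multiplies the last quarter by four (the plan has no such step). The reader recovers 4f of D:

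| Assumed f | Share of D recovered |
|---|---|
| 0.10 | 40% |
| 0.20 | 80% |
| 0.25 | 100% |
| 0.40 | 160% |

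Only f = 0.25 is free of error, and the documents give no basis for any particular f. If D(0-9) has the opposite sign to D(9-12) and is larger, the conclusion reverses.

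**Step 6: coverage after the change.** Forms at Months 3, 6, 9 and 12 on their nominal dates give 4 x 3 = 12 of 12 months. With a fixed recall the windows matter. Month 3 at +21 days and Month 6 at -7 days are 91 - 28 = 63 days apart, so 91-day recalls overlap by 28 days. Month 3 at -7 and Month 6 at +21 are 91 + 28 = 119 days apart and leave a 28-day gap.

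**The case against.** The strongest reply is that the plan never promises 12-month costs. The synopsis attaches averaging across 12 months to vIGA, POEM, DLQI/CDLQI and EQ-5D, but not to utilization and cost. The objectives table in section 3 gives Aim 3 no period and justifies the CSI as a snapshot of service use. Read that way, Aim 3 is a late-follow-up comparison, and randomization makes it valid for that window. This stands: the 12-month horizon is inferred from the trial's length and from an undated total. What remains is that the period is undefined, and that the stated cost-saving goal and cost-minimization method invite the longer reading.

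A reader might infer something stronger: that the arms differ most soon after randomization, so the design misses most of any saving or understates use by a calculable amount. The documents do not support this. Recruitment draws on patients seen since 2013 (5.4.1), eligibility admits people already in care (5.1), and visit frequency is individualized (5.4.2), so many participants may not be new evaluations. No visit pattern over time is given. If use were evenly spread, the last quarter would represent the year.

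A further objection is burden: the CSI records discipline, location, reason, cost and payer, and extra forms would fall at contacts that also collect the primary endpoint. That is a real cost, and a reason to offer an alternative that needs no new data.

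**Conclusion.** The point holds as a limit on what Aim 3 can conclude. Follow-up utilization and out-of-pocket cost are observed for about 3 of 12 months (25%), the analysis text gives the cost total no period, and effect is averaged over Months 3-12. The months 9-12 comparison is sound for that window. It does not support a 12-month cost or cost-minimization conclusion. The bias in such a conclusion could favour either arm, and its size cannot be derived from the documents.

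This rests on the three-month recall being applied as section 8.1 describes it and on the CSI being the only source for Aim 3, as the documents indicate. It concerns the observation window only. It should be fixed, but the aim is secondary and the primary EASI analysis does not depend on it.

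**What to change.** Choose one of two routes and apply it to all participants.

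**(a) Observe the full year.** Mark the CSI at Months 3, 6 and 9 in the Schedule of Activities, within the existing quarterly electronic assessments. Word the recall as running from the previous form, or record service dates, so that the -7/+21 day windows neither double-count nor leave gaps. In section 9.3.3, define 12-month utilization and out-of-pocket cost as the total over the four post-baseline periods, adjusted for the baseline form. Handle missing quarters with a longitudinal model or with multiple imputation that uses the observed quarters.

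**(b) Restate the endpoint.** If enrolment is too far along for (a), define the endpoint as utilization and out-of-pocket cost in about months 9-12, and make no 12-month cost claim.

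The two definitions should not be mixed in one comparison, with some participants contributing a year and others a quarter.

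Route (a) costs an amendment to one schedule row, the recall wording and the endpoint and missing-data text in 9.3.3, plus added questionnaire burden at three existing contacts. Route (b) costs a short amendment to the endpoint wording and a narrower conclusion.

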Out-of-pocket (OOP) costs will be evaluated using a combination of t-tests, ANOVA, least squares regression, and random-effects gamma regression. Initial analyses will compare total OOP costs per visit and overall OOP costs between the two treatment groups using simple t-tests. Subsequently, multiple linear regression models will be used to assess the impact of TCH on total OOP costs while adjusting for relevant covariates such as treatment site, age, sex, baseline EASI score, and history of asthma. A sensitivity analysis will be performed using gamma regression models. Given that cost data often exhibit a skewed distribution, appropriate transformations or robust estimation methods will be applied where necessary to improve model fit and interpretability.³² Statistical significance for all analyses will be set at p<0.05, and all statistical computations will be conducted using standard statistical software such as R.

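### Month 0 service use, cost and access values are not named as covariates in section 9.3.3, and section 9.3.1 assigns a different model to access and cost

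*Combined protocol and SAP*

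**What the plan says.** **Data collected.** On the Cornell Services Index (CSI), section 9.3.3 states that "CSI data will be collected at baseline and again at 12 months". Section 8.1 describes it as covering the frequency and duration "of use of a range of services over the past three months", and as collecting "information on out-of-pocket cost to the individual and the primary method of payment". Visit counts, duration and out-of-pocket cost therefore exist at Month 0 and Month 12 over recall periods of equal length. The Schedule of Activities (1.3) has a Month 0 row beginning "Access to Care (Baseline". It also marks the follow-up access form at Month 0 and at each quarter.

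**Analyses in 9.3.3.**
- Visit counts: "Visit counts for different service categories will be analyzed through linear models, with treatment status as the primary predictor".
- Visit duration: Welch t-tests, ANOVA and "linear regression models incorporating total visit count as a covariate". Baseline duration is not named.
- Access: "Linear regression models will be used to test whether there is a difference between the groups". No covariate or time point is named.
- Out-of-pocket cost: t-tests first, then multiple regression "adjusting for relevant covariates such as treatment site, age, sex, baseline EASI score, and history of asthma". Baseline cost is not in the list.
- Patients with no follow-up CSI data have their baseline values copied into the 12-month position.

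**Analyses in 9.3.1.** Every model adjusts for site and age group. Access and cost-saving are to be tested with the longitudinal mixed model used for severity and quality of life. Section 9.3.2 sets that model out with baseline as a response at time 0, a group term and a group-by-time term.

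**The concern.** The plan adjusts cost for baseline EASI but does not name baseline cost, although the same instrument supplies it. Better access and cost-saving are part of the trial's stated goal (1.1, 4.1), and access is framed as a superiority hypothesis, so a wide interval leaves those questions open. Section 9.3.3 itself expects skewed cost data, where a chance excess of heavy users in one arm can move a mean.

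There is also a prespecification problem. Sections 9.3.1 and 9.3.3 lead to different estimates for the same endpoints: one uses baseline as a repeated response, while the other names it nowhere as a predictor. The choice between them, and whether baseline cost joins the open covariate list, could be made after the data are seen.

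**Working it through.** The plan gives no SD, effect size, correlation or power for cost, utilization or access, so there is no stated figure to reproduce. The 272 in section 9.1 belongs to the EASI equivalence comparison and does not bear on this point.

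**Inputs.** 300 patients randomized 1:1 (5.4.1, 6.2). The 15% attrition in 9.1 is borrowed here as an assumption, giving 300 × 0.85 = 255. The significance level is 0.05 (9.3.3), taken as two-sided because sidedness is not stated. The range of r from 0.1 to 0.6 is assumed.

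**Formulas, one follow-up (CSI), equal variance at both times:**
- Follow-up only: variance proportional to 1.
- Change score, which is what a group-by-time model with one follow-up estimates: 2(1 − r).
- Baseline-adjusted: 1 − r².
- Adjusted against change: (1 − r²) / [2(1 − r)] = (1 + r)/2.
- Detectable difference at 80% power, unadjusted: (1.960 + 0.842) × √(2/127.5) = 0.351 SD. Multiply by √(1 − r²) after adjustment.

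| Assumed r | Adjusted vs follow-up only | CI width factor | Detectable difference (SD) | Power, if 80% unadjusted | Adjusted vs change score |
|---|---|---|---|---|---|
| 0.1 | 0.99 | 0.995 | 0.349 | 80.4% | 0.55 |
| 0.3 | 0.91 | 0.954 | 0.335 | 83.6% | 0.65 |
| 0.5 | 0.75 | 0.866 | 0.304 | 89.9% | 0.75 |
| 0.6 | 0.64 | 0.800 | 0.281 | 93.8% | 0.80 |

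Relative to follow-up only, the change score has variance 1.8, 1.4, 1.0 and 0.8 in the four rows. Below r = 0.5 it is worse than ignoring baseline.

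**Access, if analysed as the mean of four follow-ups.** With equal correlation r between all visits, the adjusted-to-unadjusted ratio is 1 − r²/[(1 + 3r)/4]. This gives 0.97, 0.81, 0.60 and 0.49 for the same four values of r. It applies only if the Month 0 form records the same item.

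**Skewed counts.** A simulation (gamma-Poisson counts, 300 patients, 3,000 replicates) gave r between 0.47 and 0.73. Linear baseline adjustment cut the variance to between 0.77 and 0.44 of the unadjusted value, without shifting the estimate.

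**Copying baseline forward.** A copied value carries no treatment effect. With 15% copied at random in both arms, the expected effect is multiplied by 0.85: −0.60 × 0.85 = −0.51. The simulation gave about −0.51 with or without adjustment. In the lowest-correlation case the apparent r rose from 0.47 to 0.57 and the variance ratio fell from 0.77 to 0.66, so part of any gain seen under this rule would be an artefact.

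**The case against.** The strongest reply is that 9.3.1 governs. It sends access and cost to the longitudinal mixed model, in which baseline is a response, and it already requires site and age group in all models. On that reading baseline is used and the strata are not missing. Both observations are correct. A reader might infer from 9.3.3 alone that the baseline data are thrown away, or that the visit-count and access models contain nothing but treatment; the documents do not establish either. The reply does not remove the point, because 9.3.3 then specifies t-tests, ANOVA and linear regression for the same endpoints. If the mixed model is meant, a group-by-time estimate with one CSI follow-up has change-score precision, which baseline adjustment still improves on.

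Other objections also stand in part:
- Treatment as the main predictor does not mean the only one, and the cost list is open. Baseline cost is unnamed rather than excluded, so the charge is incomplete prespecification.
- The cost regression already lists baseline EASI, age, sex, site and asthma history. Its further gain is smaller than 1 − r² implies, to the extent that these explain cost.
- The content of the access forms is not given. Baseline travel and time may also predict little in the online arm.
- Under randomization the unadjusted comparison is unbiased and its interval already allows for chance imbalance. The issue is efficiency and clarity, not validity.

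**Conclusion.** The point holds in a limited form. Baseline service use, duration, out-of-pocket cost and access are scheduled at Month 0. No section names them as covariates, and 9.3.1 and 9.3.3 disagree on the model for access and cost. Adjustment for the matching baseline value is at least as precise as either alternative, apart from one degree of freedom.

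The size is conditional. For assumed r of 0.1 to 0.6 with one follow-up, the variance reduction is about 1% to 36% against a follow-up-only comparison, and less for the cost regression. Against a change score the remaining variance is 0.55 to 0.80. It is tempting to restate the upper end as a sample-size gain (1/0.64 = 1.56 times as many patients at r = 0.6), but nothing in the documents supports choosing that r, and at 0.1 the gain over follow-up only is negligible.

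This is a should-fix matter of precision and prespecification for secondary endpoints. It leaves the primary EASI analysis untouched.

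**What to change.** Reconcile 9.3.1 with 9.3.3 and name one main model for each utilization, cost and access endpoint, including its time point. Each model should contain:
- treatment;
- the baseline value of the same measure: the count for that service type, visit duration, out-of-pocket cost or, where the Month 0 form records the same item, the access value;
- site and age group, carried over from 9.3.1.

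Close the cost covariate list, use the same baseline term in the gamma sensitivity model, and label the unadjusted t-tests descriptive.

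Revise the copy-forward rule in the same edit. One option is multiple imputation of missing 12-month CSI values from arm, baseline value, site and age group, with copied baseline values kept at most as a sensitivity analysis.

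The cost is SAP wording. The CSI values are already scheduled for collection, and for access the only extra step is to check that the Month 0 and follow-up items match.
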